9.4.16 Blastocyst Survival and Re-expansion after Cryopreservation

The number and percentage of blastocysts surviving cryopreservation will be tabulated for cryopreserved cycles cumulatively, overall and by programmed/natural cycles separately. Further,

among the blastocysts that survived cryopreservation, the number and percentage of blastocysts with re-expansion will be tabulated.

9.4.17 Number of Cryopreserved Cycles

The number of cryopreserved cycles initiated (i.e. programmed cycles with subjects starting estradiol treatment and natural cycles with subjects initiating LH surge monitoring), as well as the number and percentage of cryopreserved cycles with blastocyst transfer will be tabulated. Further, the total number of blastocysts transferred in fresh and cryopreserved cycles will be tabulated.

9.4.18 Circulating Levels of Endocrine Parameters

Blood samples drawn on stimulation day 1, stimulation day 5, end-of-stimulation, and oocyte retrieval will be analyzed for AMH, FSH, LH, estradiol, progesterone, inhibin A and inhibin B. Values below the lower limit of quantification (LLOQ) will be included as LLOQ/2. Values above the upper limit of quantification (ULOQ) will be included as ULOQ.

Each endocrine parameter and the change from baseline for post-baseline measurements will be tabulated for stimulation day 1 (baseline), stimulation day 5, end-of-stimulation and oocyte retrieval. For each parameter the change from baseline will be compared between treatment groups using a log-normal model. In this model change from baseline in log-transformed measurements will be the dependent variable and the linear predictor will include treatment as factor and baseline measurement (log-transformed) as covariate. The estimated treatment difference with 95% confidence interval will be presented on the original scale of measurement (i.e. exp-transformation applied to the log-transformed measurement) and accompanied by the p-value for test of no treatment difference.

Further, a population pharmacokinetic model will be used for evaluating the effects of subject characteristics on FSH concentrations and for assessing the variability in exposure. The modelling analysis will be described in a separate modelling analysis plan and the results reported separately from the clinical trial report.

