Failure to achieve endometrial thickness ≥8 mm in the first cryopreserved cycle will result in cycle cancellation, and in the programmed cycles, administration of 100 mg IM progesterone (PROGESTERONE Injection USP, West-ward Pharmaceutical Corp or Watson Pharma, Inc.) to induce withdrawal bleeding. In subsequent cryopreserved cycles, blastocyst transfer can take place regardless of endometrial thickness at the investigator's discretion.

In both programmed and natural cryopreserved cycles, a serum βhCG test is performed 10-14 days after transfer, clinical and vital pregnancy will be confirmed by transvaginal ultrasound 5-6 weeks after transfer, and ongoing pregnancy will be confirmed by transvaginal or abdominal ultrasound 8-9 weeks after transfer.

After completion of the trial, the subject is allowed to use cryopreserved blastocysts in accordance with local guidelines and/or regulations.

Post-trial Activities

Post-trial activities cover pregnancy and neonatal health follow-up after the fresh cycle and cryopreserved cycles.

All subjects with an ongoing pregnancy obtained in the fresh cycle or in cryopreserved cycles initiated within 12 months from the start of controlled ovarian stimulation will be followed until delivery to collect information on live birth rate. Furthermore, data will be collected on neonatal health, including minor/major congenital anomalies, at birth, 4 weeks and 1 year after birth.

Optional Exploratory Analyses

For subjects who have provided a separate informed consent, a blood sample and a saliva sample for potential future genome sequencing will be collected on stimulation day 1, and a tongue coat sample for potential future microbial profiling will be collected on stimulation day 1 and at the transfer visit(s) in the fresh and cryopreserved cycles, as applicable.

Date: 25 Apr 2018 E-Study Protocol-22377; Ver. 1.0 Supersedes: None Page 10 of 159

NUMBER OF SUBJECTS

It is planned to randomize 550 subjects in a 10:1 ratio to FE 999049 and placebo, i.e. 500 subjects assigned to FE 999049 and 50 subjects assigned to placebo. Blocked randomization will be utilized to distribute the placebo subjects randomly over the trial enrollment period. It is estimated that approximately 625 subjects should be screened to achieve 550 subjects eligible for the trial.

CRITERIA FOR INCLUSION / EXCLUSION

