9.2 Analysis and Presentation of Primary and Secondary Efficacy Endpoints

Summary tables and treatment comparisons for the primary endpoint will be presented for both the mITT and PP analysis sets. In case that the mITT and ITT analysis sets are not identical (i.e. at least one subject is randomized but not exposed) the summary tables and treatment comparisons will also be presented for the ITT analysis set. As applicable for the secondary endpoints, summary tables and treatment comparisons may be presented for the mITT and PP analysis sets.

All tabulations will be presented by treatment group. Continuous variables will be presented with number of subjects, mean, standard deviation, median, inter-quartile range, minimum, and maximum. Categorical variables will be presented with number and percentage of subjects within each specific category.

All statistical tests will be performed using a two-sided test at a 5% significance level. Treatment differences will (where appropriate) be presented with 95% confidence intervals and p-values corresponding to the statistical test of the hypothesis of 'equal effect' against the alternative of 'different effect'.

Visual displays will be produced as appropriate. All primary and secondary efficacy endpoints will be listed. Listings will only be produced for the mITT.

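### Entering out-of-range hormone values as LLOQ/2 or ULOQ in the log-normal model can materially bias the treatment ratio and its 95% interval when the arms differ and a substantial, unequal share is out of range

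*SAP*

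**What the plan says.** SAP 9.4.18, repeating Protocol 9.7.3.18, covers AMH, FSH, LH, estradiol, progesterone, inhibin A and inhibin B on stimulation day 5, at end-of-stimulation and at oocyte retrieval. Two substitution rules apply. At the low end of the assay, "Values below the lower limit of quantification (LLOQ) will be included as LLOQ/2". The rule for the high end is that "Values above the upper limit of quantification (ULOQ) will be included as ULOQ". SAP 7.10 applies the same rules to the baseline samples.

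The substituted data then enter the comparison: "For each parameter the change from baseline will be compared between treatment groups". The outcome is defined as follows: "In this model change from baseline in log-transformed measurements will be the dependent variable". Its only predictors are the treatment arm and the log of the baseline value, with no term for censoring. On reporting, "The estimated treatment difference with 95% confidence interval will be presented on the original scale of measurement", with a p-value. After exponentiation this is a ratio. SAP 9.2 adds that "All statistical tests will be performed using a two-sided test at a 5% significance level".

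Neither document has a censored-data method for these values, a sensitivity analysis of the substitution, a limit on the out-of-range share beyond which the model is not reported, or a table of out-of-range counts by arm.

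**The concern.** A value below LLOQ is known only to lie below a limit, and one above ULOQ only to lie above it. Replacing it with a constant moves the arm mean by an amount that depends on how much of that arm is out of range. If both arms move equally, the ratio is unharmed. If they move unequally, the ratio is biased and the interval is centred in the wrong place.

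Unequal shares are plausible here. Protocol 7.1.18 describes these parameters as including markers of FSH exposure and effect, and withholds results after stimulation day 1 to protect the blind, so the sponsor expects at least some of them to differ by arm. Where the arms differ and some values are out of range, the shares will generally differ too.

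At stake is the accuracy of the reported effect sizes for the endocrine profile, whose characterization is a stated secondary objective. As planned, a reader of the report's comparison tables could not tell whether an estimate rests on measurements or on constants.

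**Working it through.** **The plan's own figure.** None is given for this analysis. The trial's sizing figure, at least 99% power for the primary endpoint, reproduces (99.9995% for 30% vs 3% at 500:50, pooled variance, two-sided 5%), but it does not bear on this point.

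**Inputs.** From the documents: the substitution rules and model (SAP 9.4.18), the 5% two-sided level (SAP 9.2), and 500 vs 50 women (Protocol, Number of Subjects: "It is planned to randomize 550 subjects in a 10:1 ratio to FE 999049 and placebo"). Not in the documents, so assumed: normal logs with equal SD in both arms (0.5, 0.8 or 1.2); correlation 0.5 with baseline; true ratio 1, 2 or 4; 5% to 80% of placebo below LLOQ, or 5% to 50% of FE 999049 above ULOQ.

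**Step 1: direct calculation.** Randomization balances baseline on average, so the bias in the log ratio is the FE 999049 mean shift minus the placebo mean shift. For an arm with log mean μ and log SD σ:

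- LLOQ/2, log limit l, z = (l − μ)/σ: shift = Φ(z)·(l − ln 2 − μ) + σ·φ(z)
- ULOQ, log limit u, z = (u − μ)/σ: shift = [1 − Φ(z)]·(u − μ) − σ·φ(z)

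Take a true ratio of 2, with placebo log mean 0 and FE 999049 log mean 0.693.

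*Half of placebo below LLOQ, σ = 0.5.* Placebo: 0.5 × (−0.693) + 0.5 × 0.399 = −0.147. FE 999049 (z = −1.386): 0.083 × (−1.386) + 0.5 × 0.153 = −0.039. Net +0.109, so the expected estimate is 2 × exp(0.109) = 2.23.

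*Same, σ = 0.8.* Placebo: −0.347 + 0.8 × 0.399 = −0.027. FE 999049 (z = −0.866): 0.193 × (−1.386) + 0.8 × 0.274 = −0.048. Net −0.021, giving 1.96. The sign has reversed because of the spread alone.

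*Half of FE 999049 above ULOQ, σ = 0.8.* FE 999049: −0.8 × 0.399 = −0.319. Placebo (z = 0.866): 0.193 × 0.693 − 0.8 × 0.274 = −0.085. Net −0.234, giving 1.58. With equal spread, capping always costs the higher arm more, so ULOQ substitution pulls toward no difference.

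**Step 2: simulation of the planned regression.** 600 data sets per setting, true ratio 2. Cells show the estimated ratio, with coverage of the 95% interval in brackets.

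| Out of range | SD 0.5 | SD 0.8 | SD 1.2 |
|---|---|---|---|
| Placebo below LLOQ 5% | 2.07 (89%) | 2.02 (95%) | 2.02 (94%) |
| 20% | 2.17 (75%) | 2.08 (94%) | 1.98 (95%) |
| 50% | 2.21 (72%) | 1.96 (97%) | 1.76 (87%) |
| 80% | 1.92 (98%) | 1.57 (26%) | 1.40 (8%) |
| FE 999049 above ULOQ 5% | 1.98 (92%) | 1.97 (94%) | 1.98 (94%) |
| 20% | 1.89 (79%) | 1.86 (85%) | 1.83 (88%) |
| 50% | 1.67 (6%) | 1.58 (10%) | 1.54 (28%) |

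The 50% rows agree with step 1. At a true ratio of 4, half of FE 999049 above ULOQ gives 2.68 to 3.28 (coverage 3% to 7%), and 80% of placebo below LLOQ gives 4.28, 3.09 and 2.34 across the three SDs (88%, 29%, 0%).

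**Step 3: where little or nothing goes wrong.** With a true ratio of 1 and equal shares in both arms, estimates are 0.995 to 1.004 with coverage 92% to 97%, even at 80% out of range. With 5% out of range, the largest shift is 2.067/2 = 1.034, or 3.4%, and coverage is 89% to 95%.

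**Step 4: censored-normal likelihood on the same data (SD 0.8, 200 data sets per setting).** Estimates are 1.98 to 2.03 for a true 2 and 3.97 to 4.05 for a true 4, including at 80% below LLOQ and 50% above ULOQ. Coverage is 88% to 97%, with simulation error of about 3 points.

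Step 2 left baseline unsubstituted. Separate runs at SD 0.4 and 0.7 that also substituted baseline values gave essentially unchanged results.

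**The case against.** The strongest reply is that no out-of-range problem has been shown. The documents give no LLOQ, ULOQ, log SD or expected share for any of the seven hormones. Participants have regular cycles and early-follicular FSH of 1 to 15 IU/L (Protocol 4.1.1), so nothing suggests that most placebo FSH values would be unmeasurable. This stands: the shares above are assumptions, and the size of any error is conditional on them.

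A reader might infer that placebo sits low and FE 999049 high for every hormone. The documents do not support that. The GnRH antagonist starts only once at least 3 follicles reach 10 mm, so for LH the direction may reverse.

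A reader might also take all 21 comparisons (7 hormones × 3 visits) to be 500 vs 50. Only women who reach the triggering criterion go on to oocyte retrieval (Protocol 6.1.5), so the 7 comparisons there will have fewer placebo women, and the simulated coverage does not describe them.

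SAP 9.2 already reports medians and inter-quartile ranges. An arm's median is untouched while fewer than half its values are out of range. This helps the descriptive tables but does not repair the modelled ratio or its interval.

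Finally, the simulated logs are exactly normal, which favours the censored model. That is true, but the plan makes the same log-normal assumption, and substitution fails even when it holds.

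**Conclusion.** The point holds in conditional form. When the arms truly differ and a substantial, unequal share of values is out of range, the planned ratio and interval can be materially biased: toward no difference when high FE 999049 values are set to ULOQ, and in either direction for LLOQ/2. With half of FE 999049 above ULOQ, a true 2 shrinks by 17% to 23% (1.67/2 to 1.54/2).

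A reader might infer that the estimate is wrong wherever an arm has many out-of-range values. It is not: LLOQ/2 is nearly right at SD 0.8 with half of placebo below LLOQ (1.96 for 2 and 4.03 for 4, coverage 97%), and identical arms give no bias at all. Nor is the trial's main inference at risk. SAP 9.2.1 treats these endpoints as supportive, outside the primary and live-birth hierarchy, and every simulated mean ratio with a true difference stayed on the correct side of 1.

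All magnitudes rest on the assumed normal logs, spreads, correlation and out-of-range shares. Which hormones and visits are affected cannot be determined from the documents.

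**What to change.** Amend SAP 9.4.18 before unblinding:

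- Report the percentage below LLOQ and above ULOQ by arm and visit for each hormone.
- Whenever any post-baseline value is out of range, obtain the estimate and interval from a censored-normal (Tobit) regression of log value on treatment and log baseline, left-censored at LLOQ and right-censored at ULOQ. With log baseline as a covariate, the treatment coefficient is the same for the value as for the change.
- Keep LLOQ/2 and ULOQ for descriptive tables, for the baseline covariate, and as a sensitivity analysis.
- Pre-specify a numeric threshold, for example fewer than 10 quantifiable values in an arm, below which only the proportion in range is compared.

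The cost is a few lines of SAP text and slightly more analysis work on existing data. The method relies on the log-normal assumption already in the plan, and gives no ratio where almost a whole arm is censored. If few values are out of range, the results will barely change.

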During stimulation, subjects will be monitored by transvaginal ultrasound on stimulation days 1 and 5 and thereafter at least every second day. When the leading follicle reaches a diameter of ≥14 mm, transvaginal ultrasound will be performed daily. To prevent a premature luteinizing hormone (LH) surge, 250 µg GnRH antagonist (ganirelix acetate, GANIRELIX, Merck Sharp & Dohme) will be initiated on stimulation day 5 for subjects with ≥ 3 follicles with a diameter of ≥ 10 mm. Subjects who fail to satisfy this GnRH antagonist criterion on stimulation day 5 will continue to be monitored at least every second day, and GnRH antagonist will be initiated when/if the criterion is met. The GnRH antagonist will be continued throughout the stimulation period. Triggering of final follicular maturation will be done as soon as ≥ 2 follicles with a diameter of ≥ 17 mm are observed. If there are < 20 follicles with a diameter of ≥12 mm, 10,000 IU hCG (NOVAREL, Ferring Pharmaceuticals) will be administered. If there are ≥ 20 follicles with a diameter of ≥ 12 mm or the serum estradiol concentration is ≥3,000 pg/mL (local laboratory), 4.0 mg GnRH agonist (leuprolide acetate, LEUPROLIDE ACETATE, Sandoz) will be administered, and the fresh blastocyst transfer will be canceled. If after 8 days of stimulation, the investigator judges that the triggering criterion is not likely to be reached by day 20, the cycle will be canceled. If the triggering criterion is not met after 20 days of stimulation, the cycle will be canceled.

Oocyte retrieval will take place $36h (\pm 2h)$ after triggering of final follicular maturation, and oocytes will be inseminated by IVF or ICSI $4h (\pm 1h)$ after retrieval. Rescue ICSI is not allowed. Fertilization and embryo development will be assessed. For subjects who undergo triggering of final follicular maturation with hCG and have <20 oocytes retrieved, transfer will be performed on day 5 (blastocyst stage) after oocyte retrieval. Subjects will have one blastocyst transferred if at least one good-quality (i.e. grade 3BB or above) blastocyst is available, or one or two blastocysts transferred if no good-quality blastocyst is available. Remaining blastocysts will be cryopreserved by vitrification. For subjects with ≥ 20 oocytes retrieved following hCG administration and for subjects who undergo triggering of final follicular maturation with GnRH agonist, no transfer will take place in the fresh cycle and blastocysts will instead be cryopreserved.

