3.1 Trial Design

3.1.1 Overall Design and Control Methods

This will be a randomized, double-blind, placebo-controlled, parallel groups, multicenter trial assessing the efficacy and safety of the rFSH preparation FE 999049 in subjects aged 35-42 years undergoing controlled ovarian stimulation for IVF / ICSI following a GnRH antagonist protocol. The primary endpoint is the cumulative ongoing pregnancy rate after the fresh cycle and cryopreserved cycles initiated within 12 months from the start of controlled ovarian stimulation. Thereby, the trial is designed to capture the clinical efficacy of a single controlled ovarian stimulation cycle in a more complete manner by following outcomes from both the fresh and subsequent cryopreserved cycles. Secondary endpoints include pharmacodynamic parameters of FSH action as well as efficacy and safety parameters related to controlled ovarian stimulation from the fresh cycle and subsequent cryopreserved cycles.

Controlled Ovarian Stimulation and Fresh Cycle

Subjects will be screened within 90 days prior to randomization for compliance with the inclusion and exclusion criteria. On day 2-3 of the menstrual cycle, subjects will be randomized in a 10:1 ratio to FE 999049 or placebo, and controlled ovarian stimulation will be initiated. FE 999049 and placebo will be self-administered subcutaneously using a pre-filled injection pen.

Subjects assigned to treatment with FE 999049 will receive a starting dose of 15 µg daily that is fixed for the first four stimulation days. Based on ovarian response, the dose may be adjusted by 3 µg, with dose increases implemented not more frequently than once every 2 days and dose decreases implemented per investigator's judgement. The minimum daily dose is 6 µg, and the maximum daily dose is 24 µg. Subjects assigned to placebo will have the injection pen dialed to the same value (dose) as if administered FE 999049. Subjects can be treated with FE 999049 or placebo for a maximum of 20 days. Coasting, use of dopamine agonist or any other drug to prevent early OHSS with the exception of GnRH agonist for triggering of final follicular maturation, are not allowed.

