3.2 Determination of Sample Size

The proposed sample size of 550 (FE 999049:placebo = 500:50) can adequately address both the efficacy and safety objectives of the trial:

- The cumulative ongoing pregnancy rate in the FE 999049-treated subjects aged 35-42 years is estimated to be approximately 30% according to results from clinical trials conducted in the U.S.¹ By comparison, the pregnancy rate in the placebo arm is expected not to exceed 3%, the monthly spontaneous pregnancy rate in infertile women.² Therefore, the proposed sample size of 550 (FE 999049:placebo=500:50) will provide at least 99% power for the primary efficacy comparison. Based on the estimated cumulative ongoing pregnancy rate, the cumulative live birth rate from the fresh and/or cryopreserved cycles is estimated to be approximately 27%, resulting in a power for the comparison of the cumulative live birth rate to be at least 99%.
- A key pharmacodynamic parameter in subjects aged 35-42 years is cycle cancellation due to poor follicular development, which may occur in approximately 5% of the population exposed to gonadotropins.
- The safety and tolerability of daily rFSH preparations as part of an ART treatment cycle have been well documented for the population studied in previous clinical trials.^{3,4} OHSS was reported to occur in 1.7% to 3.7% of the subjects, with moderate/severe OHSS occurring in 1.4% to 2.2% of the subjects. Other adverse events were pelvic pain, pelvic discomfort and headache, with those assessed to be related to trial treatments reported in 1.5% to 7.1% of the subjects.

Table 1 shows that the planned sample size of 500 subjects exposed to FE 999049 provides a high probability to detect a rare adverse event or safety signal occurring in 0.5% or more subjects.

Incidence rate of rare event	Chance of detecting at least 1 event
0.5%	91.8%
0.6%	95.1%
1%	99.3%

Table 1Probabilities to Detect at Least One Rare Event

Table 2 presents the margin width estimates of the 95% confidence intervals for a range of adverse event rates with the planned sample size.

Adverse event rate	Margin of error width estimate
5%	1.9%
10%	2.6%
15%	3.1%
20%	3.5%

Table 2Estimated Margin Widths of 95% Confidence Intervals

4 Subject Disposition

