For subjects with cycle cancellation prior to triggering of final follicular maturation, the numbers of oocytes retrieved, metaphase II oocytes, fertilized oocytes, and blastocysts on day 5 will be imputed as zero.

Missing values will not be imputed for any of the other secondary endpoints, unless otherwise noted.

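### The endocrine model in SAP 9.4.18 names no variance structure; at 500:50 an equal-variance fit errs in either direction if the arms differ in spread (type I error about 10% at an assumed placebo/FE SD ratio of 1.25).

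*SAP*

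**What the plan says.** SAP 9.4.18, which matches protocol 9.7.3.18 on the model, covers AMH, FSH, LH, estradiol, progesterone, inhibin A and inhibin B. Samples are taken at baseline, stimulation day 5, end-of-stimulation and oocyte retrieval. For each parameter "the change from baseline will be compared between treatment groups using a log-normal model". The outcome is the change in log values, and "the linear predictor will include treatment as factor and baseline measurement (log-transformed) as covariate". The estimate is back-transformed, given with a 95% confidence interval, and "accompanied by the p-value for test of no treatment difference". The sections define the mean terms only; they mention no residual-variance structure, robust standard error or degrees-of-freedom method.

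Other relevant statements:

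- SAP 3.1.1: "subjects will be randomized in a 10:1 ratio to FE 999049 or placebo". SAP 3.2 gives the planned arms as 500 and 50.
- SAP 9.2: "All statistical tests will be performed using a two-sided test at a 5% significance level".
- SAP 9.2.2: "Missing values will not be imputed for any of the other secondary endpoints, unless otherwise noted". The endocrine values fall under this rule.
- SAP 9.4.18: values below the lower limit of quantification enter as half that limit, and values above the upper limit enter as that limit.
- SAP 9.2.1: analyses of the secondary efficacy endpoints are supportive and carry no multiplicity adjustment.

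**The concern.** A linear model with treatment and baseline, fitted in the usual way, estimates one residual variance from both arms. Under 10:1 allocation that estimate comes almost entirely from FE 999049, while the uncertainty of the treatment difference comes almost entirely from placebo. If the arms differ in spread, the standard error is therefore taken from the wrong arm. It is too small where placebo is the more variable arm and too large where it is the less variable.

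The design gives reasons not to presume equal spread:

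- Protocol 3.1.2 titrates FE 999049 to ovarian response between 6 and 24 µg, while placebo women only have the pen dialed as if dosed.
- GnRH antagonist starts on a follicle count. Protocol 3.1.2: "Subjects who fail to satisfy this GnRH antagonist criterion on stimulation day 5 will continue to be monitored at least every second day". Suppression of LH may therefore differ between arms.
- Substitution at the assay limits may compress the spread in whichever arm lies near a limit.

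The first two reasons act only after stimulation day 5, because protocol 3.5.2 places that assessment before any dose adjustment and before antagonist start.

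At stake are the width of the intervals and the p-values for up to 21 comparisons (7 hormones × 3 post-baseline visits). They serve the secondary objective of characterizing the endocrine profile.

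**Working it through.** **Inputs from the documents.** Two-sided alpha of 5% (SAP 9.2); n_F = 500 and n_P = 50 (SAP 3.2); model terms treatment and log baseline (SAP 9.4.18).

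**Assumed input.** r = placebo residual SD divided by FE 999049 residual SD, on the log scale. The documents give no endocrine SD for either arm, so r is varied from 0.8 to 1.5. The FE 999049 residual SD is set to 1 without loss of generality.

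**Plan's own figure.** The only figure for these tests is the nominal 5%. The formula below returns it at r = 1. The stated power of at least 99% (SAP 3.2) concerns pregnancy and live birth rates and has no bearing here.

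**Why allocation matters.**

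- FE 999049 weight in the pooled variance: 499/548 = 91%.
- Placebo share of the true sampling variance at equal SDs: (1/50)/(1/500 + 1/50) = 0.020/0.022 = 91%.

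**Formulas.**

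- Pooled variance: s² = (499 + 49r²)/548
- Model SE = √[s² × (1/500 + 1/50)] = √(0.022 s²)
- True SE = √(1/500 + r²/50)
- Type I error ≈ 2 × [1 − Φ(1.964 × model SE/true SE)], with 1.964 the t quantile on 547 df
- Coverage of the 95% interval = 1 − type I error, whatever the true difference

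**Worked case, r = 1.25.** s² = (499 + 49 × 1.5625)/548 = 575.56/548 = 1.050. Model SE = √(0.022 × 1.050) = 0.152. True SE = √(0.002 + 0.03125) = 0.182. The SE ratio is 0.834, and 1.964 × 0.834 = 1.64, so the type I error is 10.2%.

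| r | s² | Model SE | True SE | Type I error, formula | Type I error, simulated | Coverage |
|---|---|---|---|---|---|---|
| 0.8 | 0.968 | 0.146 | 0.122 | 1.9% | 1.9% | 98% |
| 1.0 | 1.000 | 0.148 | 0.148 | 5.0% | 5.0% | 95% |
| 1.25 | 1.050 | 0.152 | 0.182 | 10.2% | 10.2% | 90% |
| 1.5 | 1.112 | 0.156 | 0.217 | 15.7% | 15.7% | 84% |

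The simulation fitted the ANCOVA with log baseline to 100,000 trials per ratio at 500:50.

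**Meaning of spread.** r is a ratio of SDs. If placebo exceeded FE 999049 by 25% in variance instead, r = √1.25 = 1.118 and the type I error is 7.3% (simulated 7.5%).

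**Fewer placebo women.** Endocrine values are not imputed, so later visits can have fewer than 50 placebo women. With assumed analysed numbers:

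| FE:placebo | r = 0.8 | r = 1.25 | r = 1.5 |
|---|---|---|---|
| 475:30 | 1.7% | 10.6% | 16.8% |
| 475:20 | 1.6% | 11.0% | 17.5% |

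**Effect of the fix.** With a separate variance per arm and Welch-type degrees of freedom, the simulated type I error at 500:50 is 5.1% at r = 0.8, 5.0% at 1.25 and 5.0% at 1.5. HC3 errors with t on about 49 df gave 4.3% to 5.5% in a smaller simulation (4,000 trials per ratio, r from 0.5 to 2.0).

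**Cost where few placebo women contribute.** If only 5 placebo women reached oocyte retrieval (an assumption), their variance has 4 df. The critical value is then about 2.78 instead of 1.96, and 2.78/1.96 = 1.42, so the interval is about 40% wider even with equal variances.

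**The case against.** Four arguments can be made against this point.

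1. *The plan does not prescribe a common variance.* This is correct: the sections fix the mean model and are silent on variance. A reader might infer that the sponsor chose an equal-variance test, and the text does not support that. What stands is an omission whose ordinary default is the equal-variance fit.

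2. *The SD ratio is assumed.* Also correct. A reader might infer that the intervals have the wrong width, or that the test is liberal. The documents support neither as a statement of fact. FE 999049 could well be the more variable arm for estradiol and the inhibins, because it mixes poor and high responders, and the test would then be conservative. Only the conditional statement holds.

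3. *The antagonist rule is a thin mechanism.* It cannot act on day 5, and the protocol says nothing about the spread of LH or progesterone in placebo women. At oocyte retrieval only women who met the triggering criterion are sampled. The rule is thus a reason not to presume equal spread at later visits, but no evidence of which arm varies more.

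4. *Nothing confirmatory depends on it.* SAP 9.2.1 makes these analyses supportive and unadjusted. SAP 9.1.1 describes the ovarian-response endpoints as additional characterization. SAP 9.2 has SDs and quartiles tabulated by arm for continuous variables, so unequal spread could be seen. This limits the importance of the point, but a reported 95% interval should still have close to 95% coverage, and a descriptive table does not correct it.

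**Conclusion.** The point holds as a conditional and inexpensive improvement. As ordinarily fitted, the model in SAP 9.4.18 and protocol 9.7.3.18 relies on equal residual variances under an allocation that gives little protection if they are unequal. At 500:50 the nominal 5% test has a type I error of about 1.9% to 16% over assumed placebo/FE SD ratios of 0.8 to 1.5, and about 10% at 1.25. Coverage of the 95% interval runs from about 98% down to 84% over the same range. The direction may differ between hormones and visits.

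This rests on three assumptions: the default equal-variance fit, the SD ratio (for which the documents give no data), and about 50 placebo women contributing.

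A reader might infer that the trial's efficacy conclusion is at risk. It is not. Cumulative ongoing pregnancy and cumulative live birth are tested by other methods, and the endocrine comparisons lie outside that hierarchy.

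**What to change.** In SAP 9.4.18, with the same wording carried into protocol 9.7.3.18 if that is amended, keep the mean model and add that the residual variance is estimated separately for each arm. Satterthwaite or Kenward-Roger degrees of freedom would then apply to the 95% interval and p-value. HC3 standard errors with matching small-sample degrees of freedom are an acceptable alternative.

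Add that descriptive statistics only are presented at any visit where few placebo women contribute, with the threshold fixed before unblinding. Oocyte retrieval is the visit most likely to be affected.

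The change takes a sentence or two in the SAP and one option in the program, and needs no new data. With about 50 placebo women almost nothing is lost if the variances are equal. The cost is wider intervals where placebo numbers are small, as in the five-woman case above, which is why the descriptive-only rule belongs with it.
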